----------------------------	---

CONFIDENTIAL

STUDY DRUG(S): EVEROLIMUS
FINAL PROTOCOL DATE: 19 JUNE 2014

SCRI INNOVATIONS STUDY NUMBER: BRE 212
VERSION 1.0

BRE 212 PROTOCOL SYNOPSIS

Correlative Testing:	For patients who participate in the exploratory biomarker research component of this study, archival tumor tissue will be collected and assayed for selected biomarkers. VeriStrat Assay Serum samples will be collected from all patients at baseline and subsequent selected time points, for performing the VeriStrat assay. Treatment options for this study will not be based on the results of this testing. For details regarding the assay and sample collection, refer to Section 7.3.4 and Appendix F.
Statistical Methodology:	Results from the recently published BOLERO-2 study reported a median PFS of 2.8 months (as assessed by the treating investigator) that improved to 6.9 months as a result of the addition of everolimus in patients treated with exemestane after failing the NSAI therapy (Baselga J. et al. 2012). A similar median PFS is predicted in this study's study population that is based on similar inclusion criteria. It is anticipated that everolimus in combination with the last anti-estrogen therapy that the patient demonstrated disease progression to, will result in an increase in median PFS from 2.8 months to 5 months in this refractory population. Based on the above assumptions, given a follow-up period of 12 months after the completion of enrollment (18 months), with a 5% alpha and a one-sided test of hypothesis, a sample size of 42 will provide 80% power to detect an improvement in median PFS from 2.8 months to 5 months in the patients treated with the combination of everolimus with anti-estrogen therapy. Allowing for 8-10% invaluable patients, the total number of patients to be enrolled is 46 patients.

CONFIDENTIAL

STUDY DRUG(S): EVEROLIMUS
FINAL PROTOCOL DATE: 19 JUNE 2014

SCRI INNOVATIONS STUDY NUMBER: BRE 212
VERSION 1.0

BRE 212 CONTACT INFORMATION

SCRI Innovations Contact Information:	SCRI Innovations [name] [name] [name] [contact]
Study Chair:	[name]. Sarah Cannon Research Institute [name] [name] [name] [contact]
Safety Dept. Fax #: Safety Dept. Email:	[name] [contact]
Regulatory Phone # Regulatory Email:	[name] [contact]

CONFIDENTIAL

STUDY DRUG(S): EVEROLIMUS
FINAL PROTOCOL DATE: 19 JUNE 2014

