5.2 Correlative Studies

Archival tumor tissue blocks, if available, will be collected and assayed for selected biomarkers. Details regarding sample submission will be provided in a separate lab manual.

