7.2 Baseline Study Assessments

The following information will be collected and procedures will be performed for each patient at screening:

- Informed consent form prior to performing any study related procedures
- Medical history
- Physical examination (PE), including measurements of height (baseline visit only), weight, and vital signs (resting heart rate, blood pressure, respiratory rate, oral temperature)
- ECOG PS (See Appendix A)
- Single ECG
- Concomitant medication review
- CBC including 3-part differential and platelets
- CMP to include: glucose, BUN, creatinine, sodium, potassium, chloride, calcium, CO2, alkaline phosphatase, AST, ALT, total bilirubin, total protein, and albumin (may be done up to 72 hours prior to treatment)

CONFIDENTIAL

STUDY DRUG(S): EVEROLIMUS
FINAL PROTOCOL DATE: 19 JUNE 2014

SCRI INNOVATIONS STUDY NUMBER: BRE 212
VERSION 1.0

- Fasting serum glucose
- Fasting cholesterol, HDL, LDL, and triglycerides
- HBV-DNA, HBsAg, HBc-Ab, and HBs-Ab serologic markers (applies only to patients with risk factors)
- HCV RNA testing (applies only to patients with risk factors)
- PT or INR, and PTT (if abnormal, repeat as clinically indicated)
- Serum pregnancy test for all pre/peri menopausal women (regardless of ovarian suppression)
- Urinalysis
- Blood sample for the VeriStrat® assay (See Appendix F)
- Block of archived tumor tissue if available (slides acceptable, see lab manual for details)
- CT scan of chest
- CT scan of abdomen and pelvis
- Bone scan (if abnormal, must be repeated at restaging)

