Appendix D: Schedule of Assessments (continued)

- a The physical examination including neurological examination, update of medical history, ECOG PS, CBC, CMP plus uric acid, magnesium, phosphorus, and PT or INR, PTT must be done \leq 7 days prior to initiation of treatment. However, if these initial examinations are obtained within 72 hours of Cycle 1 Day 1 they do not have to be repeated. Scans to document measurable or evaluable disease (i.e., tumor measurement) must be performed \leq 4 weeks prior to initiation of treatment.
- b Physical examination will include measurements of height (to calculate body surface area [BSA]), weight, and vital signs (resting heart rate, blood pressure, respiratory rate, oral temperature) at the Pre-Treatment Visit. Physical examinations (PE) done at all other times during the study will include only measurements of vital signs and weight.
- c Study drug compliance will be assessed at each patient visit. The study staff will count and document the amount of study drug taken and returned by the patient.
- d CMP will include measurements of glucose, BUN, creatinine, sodium, potassium, chloride, calcium, CO₂, alkaline phosphatase, AST, ALT, total bilirubin, total protein, and albumin.
- e Patients must fast at least 8 hours overnight prior to collection of the blood specimen.
- f Cholesterol/HDL/LDL/triglycerides do not need to be repeated on Cycle 1 Day 1 if they are normal at baseline. Repeat on Day 1 of every odd cycle.
- g If PT or INR, and PTT are normal at baseline they do not need to be repeated. Patients requiring the initiation of an anti-coagulation therapy during study treatment should have their coagulation test performed as clinically indicated.
- h A serum pregnancy test for all pre/peri menopausal women (regardless of ovarian suppression) is required at baseline \leq 7 days prior to date of first treatment. All pre/peri menopausal women will need a serum or urine pregnancy test every 2 cycles (8 weeks) before receiving study treatment. If a urine pregnancy test is positive, it must be followed by a serum pregnancy test.
- i Tumor specimens from the primary site or from metastatic lesions will be collected from all patients with available archived tissue. See lab manual for details.
- j Scans are required every 2 cycles, prior to the start of odd-numbered cycles beginning with Cycle 3. Bone scans that are abnormal at baseline must be repeated at restaging.

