1.7 Coding	
 Adverse Events  Medical History	 MedDRA:  Version  Most current release and update coding with new major releases  NCI-CTCAE Version 4.03
 Concomitant Medication  Prior Therapy  Subsequent/Further Therapy	 WHO-Drug:  Version  Most current release and update coding with new major releases

2 Analysis Population	
Intent-To-Treat (ITT) Population definition:	 All patients who have started treatment in the study  All patients who have been randomized in the study, regardless of whether they have received any treatment or not  All patients who have been randomized and have started treatment in the study  Other definition, specify:
Per Protocol (PP) Population to be used in analysis:	 Yes  No If yes, please specify the criteria for exclusion from the PP population:
Safety (SAF) Population definition	 All patients who have started treatment in the study. Patients will be analyzed according to the actual treatment they have received.  Other definition, specify: All patients who have received any dose of study treatment.
Other Analysis Population definition:	Efficacy Evaluable (EE): All patients who receive at least 1 cycle of study treatment and have at least one post-baseline assessment. (Patients who discontinue treatment during Cycle 1 will not be replaced in the study.)
3 Baseline Value Definitions	
	Last value prior to first date of study treatment
4 Efficacy	
Response Criteria Used:	 RECIST 1.0  RECIST 1.1  Cheson 2007  Modified RECIST – specify:  Other criteria, Specify:

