Table 11	Any Treatment-Emergent Adverse Event by System Organ Class and Preferred Term	System organ class, Preferred term, CTCAE grade [all statistics: (n, %)]	Safety
Table 12	Any Treatment Related-Emergent Adverse Event by System Organ Class and Preferred Term	System organ class, Preferred term, CTCAE grade [all statistics: (n, %)]	Safety
Table 13	Any Treatment Related-Emergent Adverse Event by SCRI Grouped Adverse Event Term	SCRI grouped AE term, CTCAE grade [all statistics: (n, %)]	Safety
Table 14	Treatment Serious-Emergent Adverse Event by System Organ Class and Preferred Term	System organ class, Preferred term, CTCAE grade [all statistics: (n, %)]	Safety
Table 15	Treatment Related and Serious-Emergent Adverse Event by System Organ Class and Preferred Term	System organ class, Preferred term, CTCAE grade [all statistics: (n, %)]	Safety
Table 16	Duration of Response (DOR) (Kaplan-Meier estimates & 95% CI)	Number of patients with events, Number of patients censored, Duration of Response: Median [months (95% CI)] Duration of Response Estimates [probability, (95% CI)]: 4 months, 6 months	Efficacy Evaluable, Safety
Table 17	Median Follow-up (Kaplan-Meier estimates & 95% CI)	Number of patients with events, Number of patients censored, Median Follow-up [months (95% CI)] 25% Percentile Follow-up [months (95% CI)] 75% Percentile Follow-up [months (95% CI)] Follow-up Estimates [probability, (95% CI)]: 4 months, 6 months, 12 months	Efficacy Evaluable
Table 18	Genetic Abnormalities	Patients with: Any abnormality (n, %) Abnormality in PI3K/Akt/mTOR pathway (n, %) ESR1 abnormality (n, %)	Safety

Figure No	Description	Variables/Analyses To Be Included	Population
Figure 1	Overall Survival	Timescale to be used on horizontal axis:  Day  Week  Month  Year	Efficacy Evaluable, Safety
Figure 2	Progression-free Survival	Timescale to be used on horizontal axis:  Day  Week  Month  Year	Efficacy Evaluable, Safety

Listing No.	Title	Variables/Analyses To Be Included	Population
1	Prior Systemic Therapy	Patient Number Start Date End Date Medication Taken Regimen Number Disease Setting Best Overall Response Reason Therapy Ended - Specify	Enrolled Patients

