2	Current Hormonal Therapy	Patient Number Visit Name Disease Setting Medication Taken Start Date End Date Reason for Therapy End	Enrolled Patients
3	Biodesix Information	Patient Number Age Sex Race Ethnicity Performance Status at Screening (ECOG) ER (most recent) PR HER 2 Current Endocrine Therapies Prior Endocrine Therapies Prior Adjuvant Therapies Prior Metastatic Therapies Prior Neoadjuvant Therapies Disease Stage at Diagnosis Date of Treatment Start Best Overall Response Date of Best Overall Response PFS (months) OS (months)	Enrolled Patients
4	Patients with ESR1 Mutation	Patient Number	Safety, whose Tissue Samples were Assessed

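### SAP Table 18 reports genetic abnormalities as a percentage of the Safety population, but tissue is tested only where available, so any non-zero percentage is too low if a treated patient is untested

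*SAP*

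**What the plan says.** SAP Table 18 (Genetic Abnormalities) has three rows, each a count and a percentage: any abnormality, the pathway row "Abnormality in PI3K/Akt/mTOR pathway (n", %), and an ESR1 abnormality. The last row and the population entry read "ESR1 abnormality (n, %) Safety". The shell has no row for patients assessed, not assessed or missing, and no footnote naming another denominator.

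SAP Section 2 defines the Safety population as "All patients who have received any dose of study treatment". It requires neither tissue nor a test result.

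The protocol makes tissue conditional in four places:

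- Section 5.2: "Archival tumor tissue blocks, if available, will be collected and assayed for selected biomarkers".
- Section 7.2, baseline list: "Block of archived tumor tissue if available".
- Appendix D, note i: specimens "will be collected from all patients with available archived tissue".
- Synopsis, Correlative Testing: "For patients who participate in the exploratory biomarker research component of this study, archival tumor tissue will be collected".

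Archived tissue is not among the inclusion criteria in Protocol Section 3.1. SAP Listing 4 (Patients with ESR1 Mutation) has the population "Safety, whose Tissue Samples were Assessed".

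**The concern.** A percentage with Safety as its population is ordinarily the count divided by the Safety N. If only some treated patients have tissue tested, the others can never reach the numerator but still count in the denominator. The table then treats not tested as the same thing as tested with nothing found. Because no number assessed is reported, a reader of the table cannot undo the dilution.

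The qualifier on Listing 4 shows that the SAP's authors expected the assessed patients to be a subset of Safety. The listing needs no denominator and carries the restriction. The table needs one and does not.

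At stake is the reported frequency of PI3K/Akt/mTOR and ESR1 abnormalities. Table 18 is the only SAP table that describes them, and someone planning a later study could take the percentage at face value.

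**Working it through.** The documents state no figure for Table 18, so there is nothing to reproduce. The check is denominator arithmetic.

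**Inputs**

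- N, the Safety N: taken as 46, the planned enrolment (Protocol Section 5). This is an assumption and an upper bound, since a patient enrolled but never dosed is not in Safety.
- T, the number of Safety patients with tissue assessed: not given. A range from 23 to 46 is assumed.
- x, the number with an abnormality: not given. For illustration it is set to the whole number nearest 40% or 20% of T. Both percentages are assumptions.

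**Formula**

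x/N = (x/T) × (T/N)

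The literal Table 18 percentage is therefore the frequency among tested patients multiplied by T/N. If all three results come from the same tested patients, all three rows shrink by the same factor.

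**Results with N = 46**

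| Tested T | Factor T/N | About 40%: x/T | x/N | About 20%: x/T | x/N |
|---|---|---|---|---|---|
| 46 | 1.00 | 18/46 = 39.1% | 39.1% | 9/46 = 19.6% | 19.6% |
| 42 | 0.91 | 17/42 = 40.5% | 37.0% | 8/42 = 19.0% | 17.4% |
| 37 | 0.80 | 15/37 = 40.5% | 32.6% | 7/37 = 18.9% | 15.2% |
| 32 | 0.70 | 13/32 = 40.6% | 28.3% | 6/32 = 18.8% | 13.0% |
| 28 | 0.61 | 11/28 = 39.3% | 23.9% | 6/28 = 21.4% | 13.0% |
| 23 | 0.50 | 9/23 = 39.1% | 19.6% | 5/23 = 21.7% | 10.9% |

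The factor does not depend on how common the abnormality is. It equals 1 when everyone is tested, and a count of zero stays at 0% whatever T is.

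**What x/N measures**

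The status of the N − T untested patients is unknown. The proportion abnormal in the whole Safety set therefore lies between x/N (none of them abnormal) and (x + N − T)/N (all of them abnormal). With x = 13, T = 32 and N = 46, that is 13/46 = 28.3% to (13 + 14)/46 = 27/46 = 58.7%. The literal Table 18 figure is the lowest value the data allow.

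**The case against.** The strongest reply is that the SAP never writes out the percentage formula. Its population column names an analysis set, which need not be the working denominator. Table 16 (Duration of Response) lists Efficacy Evaluable and Safety, yet only responders enter it, so Table 18 might likewise mean Safety patients with a result. The first half stands: the Safety denominator is read from the column and not stated in words. The comparison with Table 16 does not hold, because SAP Section 1.2 expressly narrows duration of response to patients with CR or PR. No text narrows Table 18. Table 7 also shows that rows for not evaluable and missing were provided where they were wanted.

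Several stronger readings are tempting, and the documents do not support them:

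- **Every reported prevalence is understated.** This needs at least one untested Safety patient and a non-zero count. The conditional tissue wording makes untested patients likely, but no document gives the number tested.
- **The SAP contradicts itself.** Listing 4 has one field, the patient number, and no denominator. Anyone listed as mutated was necessarily assessed. The two population entries are inconsistent in wording, but the listing contains no percentage for Table 18 to conflict with.
- **The study's rationale is put at risk.** Protocol Section 1.3 hypothesises that pathway activation drives resistance. Tissue genetics is not a stated objective or endpoint; the only exploratory objective is the VeriStrat assay. No test, subgroup or decision uses Table 18.
- **The corrected percentage is the true prevalence.** Tissue depends on availability and, in the synopsis, on participation, so the assessed patients may be a selected group.

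**Conclusion.** The point holds as a defect in one table shell. Programmed as written, Table 18 counts untested patients as having no abnormality. Each non-zero percentage is then T/N times the frequency among assessed patients if anyone in Safety is untested.

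The size cannot be fixed from the documents. On the assumed N of 46 it runs from no effect at 46 tested, through a factor of 0.91 at 42 and 0.70 at 32, to a halving at 23. The conclusion rests on reading the population column as the denominator, which is the ordinary reading of a shell with no other instruction, and on some treated patients lacking assessed tissue. The output is descriptive and exploratory. PFS, response and safety results do not depend on it.

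**What to change.** - Set the Table 18 population to the Listing 4 entry, "Safety, whose Tissue Samples were Assessed".
- Add rows for the number assessed and the number not assessed, so that the two sum to the Safety N.
- Use the number assessed as the denominator. If pathway and ESR1 results can be missing separately, give each assay its own denominator.
- Label the percentages as frequencies among assessed patients, with a footnote that these patients may be a selected subset of those treated.

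The cost is one edit to a table shell and a smaller denominator, so each percentage rests on fewer patients. Table 18 specifies no confidence intervals, so no planned interval changes. No new data are needed beyond a record of whose tissue was assessed, which Listing 4 already requires.
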